8.1 General Principles

All analyses will be conducted using two-sided tests with a significance level of 0.05.

Statistical analyses will be performed using R or SPSS.

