3.1 Primary Objective

To establish a multicenter, cross-etiology FOG cohort and to characterize longitudinal changes in FOG burden across different underlying diseases.

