3.2 Secondary Objectives

To identify etiological and phenotypic differences in FOG progression and outcomes.

To determine risk factors and predictors for incident FOG in patients at high risk.

To describe associations between real-world treatment exposures (pharmacological, neuromodulation, rehabilitation) and changes in FOG burden.

To develop and validate multimodal prediction and risk-stratification models based on clinical, gait, video, neuroimaging, electrophysiological, and speech features.

4. Study Population

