4.1 Study Groups

FOG Group (n ≈ 500):

Patients with established freezing of gait.

High-Risk Group (n ≈ 200):

Patients with Parkinson's disease (PD) presenting gait or balance impairment but without FOG at baseline.

Total planned enrollment: 700 participants

Study centers: 1 coordinating center and 4 participating centers

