4.2 Inclusion Criteria

- 1) Age 30–85 years
- 2) Presence of freezing of gait or non-freezing gait or balance impairment
- 3) Diagnosis of Parkinson's disease or related parkinsonian disorders according to established international criteria (including PD, PSP, MSA, DLB, CBD, vascular parkinsonism, or idiopathic normal pressure hydrocephalus)
- 4) Ability to complete gait and balance assessment tasks independently or with assistance
- 5) Ability and willingness to provide written informed consent

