7.1 Primary Outcome

Longitudinal change in FOG burden, measured by annualized change in NFOG-Q

total score over 36 months.

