8.2 Primary Analysis

Linear mixed-effects models will be used to evaluate longitudinal changes in FOG burden and to compare trajectories across etiological subgroups.

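### Does the general 0.05 level leave the comparison of trajectories across etiologies with a false-positive risk of 41–44%?

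*Protocol*

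**What the plan says.** Section 8.1 of the protocol, under general principles, gives one sentence on error rates: "All analyses will be conducted using two-sided tests with a significance level of 0.05". It adds nothing about multiplicity in either direction.

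Section 8.2 assigns linear mixed-effects models to the primary analysis, to describe change in FOG burden and to "compare trajectories across etiological subgroups". It does not say whether this is one joint test, a set of contrasts against a reference, or all pairs. It does not give the number of subgroups.

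The outcome in section 7.1 is a rate of change: "Longitudinal change in FOG burden, measured by annualized change in NFOG-Q" total score over 36 months. The comparison is therefore one of slopes.

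The number seven comes from section 4.2, an eligibility criterion that admits parkinsonian disorders "including PD, PSP, MSA, DLB, CBD, vascular parkinsonism, or idiopathic normal pressure hydrocephalus".

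The primary objective in section 3.1 is to set up the cohort and to "characterize longitudinal changes in FOG burden across different underlying diseases". The search for differences between etiologies stands in section 3.2 as a secondary objective: "To identify etiological and phenotypic differences in FOG progression and outcomes". Section 4.1 gives "Total planned enrollment: 700 participants", about 500 of them with FOG, and no breakdown by diagnosis.

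**The concern.** Read together, the three sections suggest a familiar problem. One level is set for everything, the primary analysis compares groups, and seven diagnoses can enter. Seven groups form 21 pairs. If each pair were tested at 0.05 and any significant pair reported as a finding, the 5% in section 8.1 would not describe the chance of a false statement about etiology.

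Consecutive recruitment with no minimum per diagnosis adds to the unease, because some groups could be very small and their slopes poorly estimated. At stake would be a published statement that one disease progresses differently from another when it does not.

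**Working it through.** **Inputs**

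- Level: 0.05, two-sided (section 8.1).
- Comparison: slopes across etiological subgroups, form not stated (sections 7.1 and 8.2).
- Number of groups k: seven diagnoses are eligible (section 4.2); the number of analysis groups is not stated.
- Group sizes: about 500 with FOG and 700 in all (section 4.1). The split by diagnosis is not given, so it is assumed and varied below.

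The protocol states no family-wise error, power or sample-size derivation, so there is no derived figure to reproduce beyond 500 + 200 = 700.

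**Step 1: the scenario behind the concern.** All pairs of seven groups: 7 × 6 / 2 = 21 contrasts. With equal true slopes and equal group sizes, the chance that at least one unadjusted contrast is significant is the studentized-range tail P(Q > 1.96 × √2) for k = 7 and very large degrees of freedom, which is 0.4405. For unequal sizes, slope estimates were simulated as normal with variance inversely proportional to group size (400,000 draws each):

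| Assumed group sizes | Any of 21 pairs | Any of 6 versus the first group | Joint 6-df test |
|---|---|---|---|
| seven of 71 | 0.441 | 0.208 | 0.051 |
| 200, six of 50 | 0.430 | 0.253 | 0.050 |
| 300, 40, 40, 40, 30, 25, 25 | 0.420 | 0.263 | 0.050 |
| 400, 20, 20, 15, 10, 20, 15 | 0.412 | 0.264 | 0.049 |
| 470, six of 5 | 0.411 | 0.265 | 0.050 |

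The 41–44% is therefore right for 21 unadjusted pairwise tests. Treating them as independent would give 1 − 0.95^21 = 0.659, which is too high because the contrasts share groups.

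**Step 2: the other readings of section 8.2.**

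- One joint etiology-by-time test: 5% by construction, 4.9–5.1% in simulation.
- Six contrasts against one reference diagnosis, unadjusted: 21–27%.
- Fewer, pooled groups, all pairs unadjusted: 12.2% for k = 3, 20.3% for k = 4, 28.6% for k = 5, 36.6% for k = 6.
- All 21 pairs with adjustment: at most 5%. Bonferroni, for example, tests each at 0.05 / 21 = 0.00238; Holm or a Tukey-type method holds the same family level.

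Depending on the reading, the risk runs from 5% to 44%. The top of that range needs three things together: seven separate analysis groups, all pairs tested, and no adjustment. The protocol states none of the three.

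**Step 3: what section 8.1 fixes.** It fixes sidedness and a level. A joint test at 0.05 complies with it. So do adjusted p-values judged at 0.05. Only a statement that each contrast is tested at 0.05 without adjustment would turn the sentence into a faulty rule, and there is no such statement.

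**Step 4: small groups.** In the table, the most uneven split gives the lowest any-pair risk (41.1%) and equal sizes the highest (44.0–44.1%). In this calculation, small groups cost precision but do not add false positives. How small any diagnosis will be cannot be read from the protocol.

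**The case for a change.** The best case for the concern is that section 8.1 is not silent. It is a positive rule covering every analysis, and it does not set a primary test apart from the rest. A joint test shows only that some difference exists; the secondary objective of identifying etiological differences calls for contrasts sooner or later. The comparison also has a mixed status, since section 8.2 places it in the primary analysis while section 3.2 lists etiological differences as secondary. Every unadjusted multi-contrast reading exceeds 5%, even with three pooled groups, and clarification would cost only a sentence.

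Part of this stands. The protocol does not name the test, and naming the joint interaction test would do no harm. If follow-up contrasts are made, they need their own control: an unadjusted pairwise step after a significant joint test protects the error rate only when all slopes are equal.

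The rest does not follow. That contrasts may be wanted later does not make them unadjusted, and a general level of 0.05 does not forbid adjustment. The remedy that suggests itself, a joint etiology-by-time test, is already the ordinary meaning of comparing trajectories across groups in a mixed model. A minimum group size for pooling would be a matter of preference, because no figure in the protocol points to one. The study is observational, its primary objective is descriptive, and it announces no confirmatory claim of difference whose error rate section 8.1 could misstate. Even in the worst case a false finding is less likely than not.

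**Conclusion.** The concern does not hold. The 41–44% is correct arithmetic for a procedure that the protocol does not specify. Under the ordinary reading of section 8.2 the risk is 5%, and adjusted contrasts would keep it at or below 5%. Sections 8.1, 8.2 and 4.2 contain no wrong statement and do not contradict one another on this point.

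This rests on two things: section 8.2 is read as a joint comparison unless something says otherwise, and the choice of contrasts, adjustment and pooling is commonly left to the statistical analysis plan, which is not at hand. If that plan prescribed all 21 pairwise tests at 0.05 without adjustment, the 41–44% would apply and would be a criticism of that plan.

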8.2 Primary Analysis

Linear mixed-effects models will be used to evaluate longitudinal changes in FOG burden and to compare trajectories across etiological subgroups.

8.3 Secondary Analyses

Cox proportional hazards models will be used to analyze time-to-event outcomes (e.g., incident FOG, first fall).

9. Ethics and Regulatory Considerations

This study will be conducted in accordance with the Declaration of Helsinki and relevant national regulations. Approval will be obtained from the institutional ethics committee at each participating center prior to initiation.

All participants will provide written informed consent prior to enrollment.

10. Privacy and Data Protection

All data will be de-identified using coded participant IDs.

Data will be stored in encrypted systems with role-based access control.

Results will be reported only in aggregate form, without any personally identifiable information.

11. Data Retention

Study data will be retained for a minimum of 5 years after study completion, in accordance with institutional and regulatory requirements.
